### 7.4 Recording of Adverse Events

All adverse events will be recorded on a patient specific adverse event log. The AE log will be maintained by the research staff and kept in the patient’s research chart.

### 7.5 Serious Adverse Event (SAE) Reporting

#### 7.5.1. Definition of SAE

SERIOUS ADVERSE EVENTS include death, life threatening adverse experiences, hospitalization or prolongation of hospitalization, disability or incapacitation, overdose, congenital anomalies and any other serious events that may jeopardize the subject or require medical or surgical intervention to prevent one of the outcomes listed in this definition.

#### 7.5.2. Reporting of SAE to IRB

All SAEs occurring on this study will be reported to the IRB according to the

IRB policy. The IRB requires immediate reporting of all unexpected and study-related (definite or probable) adverse events. The following procedure will be followed for reporting SAE to the IRB:

- Complete the SAE Cover Sheet (See Appendix B)
- If the event is unexpected AND definitely or probably related to the study, complete the IRB Unexpected, Study-related Adverse Events, Incidents, and Information Reporting Form. This form should be submitted within 24 hours of investigator notification of the event.
- If the event is expected OR possibly or unrelated to the study, only the SAE Cover Sheet must be completed. These events will be reported to the IRB at the time of continuing renewal on the Adverse Event & IND Safety Reporting Cumulative Table.

Forms may also be downloaded from the IRB website at: [http://www.med.cornell.edu/research/for\\_pol/ins\\_rev\\_boa.html](http://www.med.cornell.edu/research/for_pol/ins_rev_boa.html)

### **7.5.3. Reporting of SAE to FDA**

If an SAE occurs on this study, the event will be filed on a MedWatch form with the FDA.

## **8. PHARMACEUTICAL INFORMATION**

A description of potential risks associated with  $^{89}\text{Zr}$ -df-IAB2M can be found in Section 7.1.

### **8.1 $^{89}\text{Zr}$ -df-IAB2M (IND#:130768)**

#### **8.1.1 Radiolabeling of $^{89}\text{Zr}$ -df-IAB2M:**

$^{89}\text{Zr}$ -df-IAB2M is produced and will be administered under IND No. 130768. For this study, IAB2M is conjugated to desferrioxamine (Df) for labeling with  $^{89}\text{Zr}$ . The final investigational drug product is  $^{89}\text{Zr}$ -df-IAB2M and is supplied as a sterile filtered solution in a sterile vial sealed with rubber septa and closed with an aluminum stopper.  $^{89}\text{Zr}$  is chelated by the Df moiety of the Df-IAB2M conjugate. No materials of animal origin are used in the manufacturing of  $^{89}\text{Zr}$ -df-IAB2M. Manufacturing of Df-IAB2M has been performed and

overseen by ImaginAb, Inc. U.S. df-IAB2M is provided by ImaginAb under IND# 118810.

The labeling of df-IAB2M with  $^{89}\text{Zr}$  is performed at Weill Cornell Medicine by [name]., Chief of Radiochemistry and the Professor of Radiochemistry/Radiopharmacy in Radiology. df-IAB2M is provided by ImaginAb, under IND# 118810. The process for the manufacture of the  $^{89}\text{Zr}$ -df-IAB2M has been submitted and reviewed as a part of the IND #130768. The radiochemistry staff at Weill Cornell Medicine will be responsible for QC testing and batch release of  $^{89}\text{Zr}$ -df-IAB2M for clinical use.

The final study drug product is 2.5 (+/- 10%) mCi of  $^{89}\text{Zr}$ -df-IAB2M formulated in solution consisting of 5% human serum albumin solution USP, 4mg/mL gentisic acid and 0.2M sodium acetate solution, aseptically mixed with df-IAB2M to achieve a total protein dose of 10 mg.

### **8.1.2 Radiopharmacy dispensation of $^{89}\text{Zr}$ -df-IAB2M:**

The Nuclear Medicine Physician or designee is responsible for ensuring that the delivery of the investigational drug product from the Radiopharmacy to the facility site for patient infusion are correctly labeled, received, handled, and stored in accordance to ICH and applicable government regulations, local/state laws, and used in accordance with this protocol.

The syringe will be shielded by secondary lead containers for radiation protection purposes. The exact radioactive dose administered must be determined by measuring the  $^{89}\text{Zr}$ -activity in the syringe before infusion and after infusion by using a dose calibrator, with radioactivity decay correction for infusion time. Measured radioactivity values and times of measurement will be documented, as well as the total injected volume. All unused study drug product must be returned to the Radiopharmacy or destroyed in accordance with institutional policies.

### **8.1.3 Availability**

df-IAB2M is an investigational agent supplied to investigators by ImaginAb. The process for the manufacture of the  $^{89}\text{Zr}$ -df-IAB2M by the Radiochemistry/Radiopharmacy Lab in the department of Radiology at Weill Cornell Medicine has been submitted and reviewed as a part of the IND # 130768.

### **8.1.4 $^{89}\text{Zr}$ -df-IAB2M Accountability**

$^{89}\text{Zr}$ -df-IAB2M Inventory Records – The investigator, or a responsible party designated by the investigator, will maintain a careful record of the inventory and disposition of all agents received from ImaginAb on a Drug Accountability Record Form (DARF).

### **8.1.5 $^{89}\text{Zr}$ -df-IAB2M Infusion**

$^{89}\text{Zr}$ -df-IAB2M will be administered under IND No. 130768. A 10 mg mass dose containing 2.5 mCi  $^{89}\text{Zr}$  labeled to 2-3 mg of df-IAB2M and 7-8mg of cold (unlabeled) df-IAB2M will be injected intravenously. The dispensed dose will be infused under the direct supervision of a Nuclear Medicine Physician or designee. Patients will be monitored for safety during and up to one hour after the injection.

Regulatory agencies require accounting for the disposition of all investigational drugs received by each clinical site. Information on drug disposition required by law consists of: 1) date received; 2) date dispensed; 3) quantity dispensed, and 4) patient identification number to whom the drug was dispensed. The Investigator is responsible for accounting for all unused study drug and all used study drug.

## **8.2 Ga-PSMA-HBED-CC (IND #124495):**

### **8.2.1 Radiolabeling of Ga-PSMA-HBED-CC:**

ABX Advanced Biochemical Compounds, Radeberg, Germany produces PSMA-HBED-CC. Upon purchase and shipment to Weill Cornell Medicine, it will be labeled with Ga with final product being Ga-PSMA-HBED-CC. Radionuclide conjugation will be done at the Division of Nuclear Medicine, Department of Radiology, Weill Cornell Medicine.

The material produced is subjected to quality assurance testing as outlined in the Food and Drug Administration “Points to Consider”. All production data and supporting documents, together with the results of all quality assurance testing, have been provided to and reviewed by the Food and Drug Administration (Ga-PSMA-HBED-CC, IND# 124495).

### **8.2.2 Radiopharmacy dispensation of Ga-PSMA-HBED-CC:**

The Nuclear Medicine Physician or designee is responsible for ensuring that the delivery of the investigational drug product from the Radiopharmacy to the facility site for patient infusion and also to make sure that it is correctly labeled, received, handled, and stored in accordance to ICH and applicable government regulations, local/state laws, and used in accordance with this protocol.

The syringe will be shielded by secondary lead containers for radiation protection purposes. The exact radioactive dose administered must be determined by measuring the Ga-activity in the syringe before infusion and after infusion by using a dose calibrator, with radioactivity decay correction for infusion time. Measured radioactivity values and times of measurement will be documented, as well as the total injected volume. All unused study drug product must be returned to the Radiopharmacy or destroyed in accordance with institutional policies.

### **8.2.3 Availability**

PSMA-HBED-CC is an investigational agent supplied to investigators by ABX Advanced Biochemical Compounds, Radeberg, Germany. The process for the manufacture of the Ga-PSMA-HBED-CC by the Radiochemistry/Radiopharmacy Lab in the department of Radiology at Weill Cornell Medicine has been submitted and reviewed as a part of the IND # 124495.

### **8.2.4 Ga-PSMA-HBED-CC Accountability**

Ga-PSMA-HBED-CC Inventory Records – The investigator, or a responsible party designated by the investigator, will maintain a careful record of the inventory and disposition of all agents received from ABX Advanced Biochemical Compounds, Radeberg, Germany on a Drug Accountability Record Form (DARF).

### **8.2.5 Ga-PSMA-HBED-CC Infusion**

Single intravenous dose of  $^{68}\text{Ga}$ -PSMA-HBED-CC ( $5 \pm 2$  mCi) will be administered under IND # 124495 on an *outpatient* basis. Intravenous access must be well established prior to initiating infusion. The injection will be given by slow intravenous bolus. Following completion of the  $^{68}\text{Ga}$ -PSMA-HBED-CC injection, a normal saline flush (approximately 10 mL) will ensure that all  $^{68}\text{Ga}$ -PSMA-HBED-CC remaining in the infusion line is injected.

## 9. IMAGING AND SPECIAL STUDIES

### 9.1 Imaging and histopathology

#### 9.1.1 3T multi-parametric pelvic MRI

##### 9.1.1.1 Method of Assessment

3T mpMRI preoperative images will be read by GU radiologist reporting: location, size and features of lesions suspicious for PCa. Lesional criteria on MR are defined as being well-circumscribed with low signal intensity on T2 weighted images with associated diffusion restriction on ADC maps. Dynamic contrast enhanced (DCE) MR imaging on preoperative images will also be evaluated subjectively for early and intense enhancement followed by rapid washout, findings that are all associated with prostate cancer. The radiologist will have access to TRUS biopsy results.

An MR /lesional analysis will be performed. Lesional criteria on MR will be defined as well-circumscribed low signal intensity on T2 weighted images with associated diffusion restriction on ADC maps. Dynamic contrast enhanced MR imaging on preoperative images will also be evaluated subjectively for early and intense enhancement followed by rapid washout, findings that are all characteristic of prostate cancer.

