#### 9.1.2 $^{89}\text{Zr}$ -df-IAB2M PET/CT imaging

##### 9.1.2.1 Method of Assessment

PET/CT will be read twice by a nuclear medicine physician. For the first interpretation, the physician will be blinded from clinical history, biopsy results and conventional

imaging modalities. After the initial reading, the nuclear medicine physician will be provided with both the TRUS biopsy results and previously read scans for the repeat PET/CT reading. During each interpretation, the physician will record all abnormal, suspicious areas with higher uptake than adjacent or contralateral background. Each abnormal area will be recorded on a map of the prostate along with maximum standardized uptake value ( $SUV_{max}$ ) and mean standardized uptake value ( $SUV_{mean}$ ).

Subsequently, the accumulation of  $^{89}Zr$ -df-IAB2M will be compared to areas of known PCa foci on histopathology and mpMRI, as described in Section 13. After completion of the histopathology, the PET/CT findings will be compared to histopathology to perform a lesion by lesion analysis with histopathology serving as the reference gold standard. This analysis will primarily include tumors  $\geq 0.5 \text{ cm}^3$  on histopathology, with a secondary assessment of any lesions  $<0.5 \text{ cm}^3$ . Similarly, areas of increased uptake identified on IAB2M, which had been read as suspicious for cancer will be compared to histopathology to determine the underlying pathology (e.g., inflammation, benign prostatic hyperplasia).

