#### 9.1.3 $^{68}Ga$ -PSMA-HBED-CC PET/CT imaging

Patient preparation should be according to the policies and procedures of the local imaging site (CIBC). The patient does not need to be fasting for either the infusion or the scans. The use of intravenous or oral contrast will not be permitted. Specifications for acquiring the  $^{68}Ga$ -PSMA-HBED-CC PET/CT scans will be provided in study specific documentation by the study chair or the co-investigators from the Division of Nuclear Medicine. PET/CT images are acquired between 1 and 3 hours after the  $^{68}Ga$ -PSMA-HBED-CC infusion. Image acquisition will be from vertex of skull to mid thighs. The subject will be scheduled for the injection and imaging between screening and prostatectomy depending on subjects' availability and compliance.

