- e Radiographic evaluations include a modified (3T multiparametric) MRI of the pelvis, if clinically indicated. Radiographic studies are to be performed within 6 weeks before, or on Visit 3/Day 2, provided the patient has not received a new intervening anti-cancer treatment.
- f Blood sample will be drawn via venipuncture for HAHA evaluation pre-infusion at Visit 3 and repeat samples will be taken at Visit 5 (week 6, +/- 1 week).
- g Ga-PSMA-HBED-CC administration followed by PET/CT scan 1 – 3 hours later must be done prior to Zr-df-IAB2M tracer administration on Visit 2 otherwise the Ga-PSMA-HBED-CC administration and PET/CT scan can be done anytime between screening and prostatectomy visit.

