### Secondary endpoints

- To determine the ability of *in vivo* Zr-df-IAb2M PET/CT to correlate with pathological features (i.e. Gleason pattern, diameter and PSMA-positivity):
  - The Wilcoxon rank sum test will be used to compare lesions that were and were not identified on *in vivo* PET with respect to lesion size, immunohistochemical PSMA staining, and Gleason score (demonstrated by histopathology). This lesion based analysis will be performed in a similar fashion as described above.
- To compare the *in vivo* Zr-df-IAb2M PET/CT and Ga-PSMA-HBED-CC PET/CT to *in vivo* mpMRI:
  - The diagnostic accuracy of Zr-df-IAB2M PET/CT and Ga-PSMA-HBED-CC PET/CT imaging in patients with prostate cancer will be compared with that of mpMRI imaging by using sector-based analysis, as described by Turkbey B et al. The estimates of patient-specific sensitivity and specificity will be defined as the proportion of true-positive sectors and the proportion of true-negative sectors in each patient. Overall sensitivity and specificity will then be estimated by calculating the mean (and standard error) of these individual-

specific estimates across patients. Differences in sensitivity and specificity between modalities will then be evaluated by the Wilcoxon signed-rank test.

- To determine the sensitivity, specificity, PPV, NPV of IAB2M to detect all pathologically identified PCa lesions that do not meet criteria for clinical significance (defined as:  $< 0.5 \text{ cm}^3$  with Gleason pattern  $< 4$ ):
  - As above, but for lesions considered not to be clinically significant.
- To correlate IAB2M positivity (SUV) and lesion size:
  - The Spearman-rank correlation coefficient will be used to evaluate the association between SUV and size of the lesion (procedure for size measurements are defined in Section 9.1.3).
- To correlate IAB2M positivity (SUV) and Gleason pattern (3, 4 and 5):
  - The Spearman-rank correlation coefficient will be used to evaluate the association between correlate SUV and the histopathologically defined Gleason pattern. The Wilcoxon rank-sum test will also be used to compare  $\text{SUV}_{\text{max}}$  measurements between lesions with low Gleason score (3+4 or lower) and high Gleason score (4+3 or higher).
- To correlate IAB2M positivity (SUV) and PSA:

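### The secondary sector-based test of 89Zr PET/CT against mpMRI does not match what the readers know: mpMRI is read with TRUS biopsy results, and no PET read is named or assured to be its equal

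*Combined protocol and SAP*

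**What the plan says.** **mpMRI read (Section 9.1.1.1).** A GU radiologist reports the location, size and features of suspicious lesions. "The radiologist will have access to TRUS biopsy results". No mpMRI read without those results is described.

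**89Zr PET/CT reads (Section 9.1.2.1).** One nuclear medicine physician reads each scan twice. "For the first interpretation, the physician will be blinded from clinical history, biopsy results and conventional" imaging modalities. Afterwards, "the nuclear medicine physician will be provided with both the TRUS biopsy results and previously read scans for the repeat PET/CT reading". The section does not list which scans these are. At each read, "the physician will record all abnormal, suspicious areas with higher uptake than adjacent or contralateral background", and marks the areas on a prostate map, so either read could supply sector calls.

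**68Ga PET/CT (Section 9.1.3).** The text covers preparation, timing and acquisition, for example "Image acquisition will be from vertex of skull to mid thighs". It gives no reading or blinding rule.

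**Analysis (Section 12.1, Secondary endpoints).** Both PET tracers are compared with mpMRI by sector. Sensitivity and specificity are computed per patient and averaged. "Differences in sensitivity and specificity between modalities will then be evaluated by the Wilcoxon signed-rank test". All tests are two-sided at 0.05. No PET read is named, here or elsewhere in Section 12.

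**Who has an mpMRI (Section 10, footnote e).** "Radiographic evaluations include a modified (3T multiparametric) MRI of the pelvis, if clinically indicated".

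**The concern.** A paired test of two imaging methods shows which images better only if the two readers know the same things. Biopsy results point to sectors that contain cancer, so a reader who has them can call sectors that the image alone would not have prompted. Here the mpMRI reader always has that help. The PET reader lacks it at the first read. At the second, the PET reader has it, and perhaps the mpMRI findings as well.

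The mismatch is in the plan as written: following the protocol exactly with the first PET read still gives an unequal comparison. The likely direction for sensitivity also depends on the read used. Because both reads are kept and no rule chooses between them, the choice could be made after the results are known.

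What is at stake is the PET-versus-mpMRI estimate. It is secondary, but Sections 12.1 and 12.2 intend the study's estimates as preliminary data for later studies. A difference in reader information does not average out as patients are added.

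**Working it through.** **The plan's own figure.** The only sizing figure is the ±19.0% half-width for the primary proportion: 1.96 × √(0.75 × 0.25 / 20) = 0.190. It reproduces, and nothing below bears on it.

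**Reader information, side by side**

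| Read | TRUS biopsy results | Other imaging |
|---|---|---|
| mpMRI (9.1.1.1) | yes | not stated |
| 89Zr PET, first (9.1.2.1) | no | blind to conventional imaging |
| 89Zr PET, second (9.1.2.1) | yes | earlier scans, not specified |
| 68Ga PET (9.1.3) | not stated | not stated |

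The first PET read has less information than the mpMRI read. The second matches it on biopsy, and matches it overall only if the mpMRI is withheld. It is not even certain that the first read is blind to mpMRI: Section 2.3 uses conventional imaging to mean CT, bone scan and FDG PET.

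**Illustrative size for sensitivity.** The documents supply none of these inputs; all are assumed.

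- s = 0.70: blinded sensitivity, equal for both scanners
- b = 0.375: share of truly positive sectors marked by biopsy, the same whether or not imaging detects them
- a = 0.50: share of missed sectors that become positive calls once the reader is told of them
- misses by the two scanners are independent

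*First PET read against informed mpMRI.* PET sensitivity is s; mpMRI sensitivity is s + (1 − s)·b·a.
Gap (PET − mpMRI) = −(1 − s)·b·a = −0.30 × 0.375 × 0.50 = −0.056, about 6 points against PET.

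*Second PET read, mpMRI withheld.* Both readers have the biopsy results, so under these assumptions the gap is 0.

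*Second PET read, mpMRI supplied.* PET also adopts, at rate a, mpMRI calls in sectors it still misses.
Gap = a·[b(1 − s)(1 − a)(s + (1 − s)a) + (1 − b)(1 − s)s]
= 0.5 × [0.375 × 0.30 × 0.50 × 0.85 + 0.625 × 0.30 × 0.70]
= 0.5 × [0.0478 + 0.1313] = 0.0895, about 9 points for PET.
Letting sensitivity vary between patients (SD 0.6 on the logit scale, shared by both scanners) lowers this slightly: averaging the formula gives 0.087, and a simulation gave 0.084. Hence 8 to 9 points.

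**How far the assumptions carry the result**

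- If biopsy mainly marks sectors that imaging already sees, the gaps shrink. Halving b among missed sectors gives 0.30 × 0.1875 × 0.50 = 0.028 for the first read, about 3 points.
- If half of the blinded calls are shared by the two scanners, the second-read gap becomes 0.5 × [0.375 × (0.15 × 0.50 × 0.50 + 0.15 × 0.50 × 0.85) + 0.625 × 0.105] = 0.5 × [0.0380 + 0.0656] = 0.052, about 5 points. The first-read gap does not change.
- High conversion rates are implausible for either reader. Section 9.1.2.1 requires raised uptake for a PET call, and Section 9.1.1.1 requires T2 and diffusion findings for an MR lesion.

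Specificity was not computed. Biopsy results could add false positive calls or remove them, so its direction is uncertain.

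**The case against.** The strongest case on the other side has four parts.

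1. *Little hangs on it.* This is one of several secondary analyses in a 20-patient study that describes itself as an exploratory pilot. The interim look in Section 12.3 uses the primary endpoint, and the pathologist is blinded to imaging (Section 9.1.4.1). This stands, and it lowers the priority.

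2. *A biopsy-informed mpMRI may be the intended comparator.* All patients have confirmed cancer, and mpMRI is done when clinically indicated, so an informed read reflects mpMRI as used in care. That is a legitimate estimand. But it needs a PET read with biopsy results and without the mpMRI, and the protocol does not assure one.

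3. *With the first read, the tilt runs against the investigational tracer.* On sensitivity this is right: that pairing would not manufacture superiority for PET. The estimate would still be distorted.

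4. *Section 12 defers to a cited study for method.* That source cannot be checked here. The reading conditions are set locally in Section 9, and the visible text names no read.

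Some stronger readings do not hold. A reader might infer that the second PET read uses the mpMRI and that the protocol therefore favours PET; the earlier scans are undefined, so this is only a possibility. A reader might infer that 68Ga PET is read under unequal conditions; they are unstated, not shown to be unequal. And a reader might take the pointer in Section 9.1.2.1 to "areas of known PCa foci on histopathology and mpMRI, as described in Section 13" as a sign of a missing analysis section. The contents list ends at Section 12, which contains the comparison, so this looks like a numbering slip.

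**Conclusion.** The mismatch is real and follows from the text. The only mpMRI read described is informed by biopsy, the first PET read is not, the second may have more information than the mpMRI read, and the test names neither. No described PET read is assured to match.

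The size is not known from the documents. Under the assumed inputs it is about 6 sensitivity points against PET with the first read. With the second read it is 8 to 9 points for PET if the mpMRI is supplied, and none if it is withheld. These figures illustrate the problem; they do not estimate the bias. The assumptions do not support quoting a false-positive rate for the signed-rank test.

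A reader might go further and conclude that the trial's main result is compromised. The documents do not support that. The primary endpoint makes no comparison with mpMRI, the sample size does not rest on this test, and the reference standard is read blind. This is a cheap improvement to a secondary, hypothesis-generating comparison.

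**What to change.** 1. **Section 9.1.1.1:** have the GU radiologist record sector calls blind to TRUS and PET results before the biopsy-informed read, as the protocol already does for 89Zr PET.
2. **Section 12.1:** state that the PET-versus-mpMRI sector test pairs this blinded mpMRI read with the first PET read. Report informed reads separately as descriptive. Give the number of patients contributing pairs, which may be below 20 because mpMRI depends on clinical indication.
3. **Section 9.1.2.1:** state that the first read is blind to mpMRI and to the 68Ga PET, and whether the scans supplied at the second read include mpMRI. Correct the section pointer. In **Section 9.1.3**, apply the same first-read rule to 68Ga PET, including blinding to the 89Zr scan.
4. **Scans already read with biopsy results:** this can happen, since mpMRI may precede Visit 3 by up to six weeks and standard-of-care evaluations within the screening window need not be repeated. Where no blinded pass was possible, flag the patient, report the comparison with and without such patients, and state the information difference as a limitation.

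**Cost:** up to about 20 short extra reading passes by the same radiologist, a blinded first read of each 68Ga scan if that is not already the practice, and possibly fewer fully blinded pairs. The rest is wording.
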